5.5 Statistical Considerations

5.5.1 Sample size

A sample size of up to 60 patients, enrolled in this proposed multi-center study, is considered adequate to further confirm the safety and performance of the Cardioband System in TR patients. Considerable clinical data on the safety of clinically equivalent devices exists, this will enable a comparison of the clinical data obtained in this study of the safety and performance of the Cardioband System, with literature data from prior studies.

5.5.2 Sample size Justification

Reference values for calculations are based on a literature review of predicate devices [REDACTED] and clinical experience in previous studies of Valtech adjustable mitral annuloplasty devices [REDACTED].

Therefore, this sample size allows accurate estimates of risk associated with the device even for rare events.

The sample size for the study was selected through the width of the two-sided exact 95% confidence interval of the potential adverse event rates. [REDACTED]

[REDACTED]	■	[REDACTED]	[REDACTED]	[REDACTED]
[REDACTED]	■	[REDACTED]	[REDACTED]	[REDACTED]
[REDACTED]	■	[REDACTED]	[REDACTED]	[REDACTED]
[REDACTED]	■	[REDACTED]	[REDACTED]	[REDACTED]

Rates for anticipated complications (adverse events) will be compared with historical data on morbidity and mortality in similar populations and for analogous devices.

5.5.3 Analysis of performance and safety endpoints

The performance and safety endpoints of the Cardioband System will be assessed by recording the echocardiographic parameters and by monitoring the patient clinical status. Safety assessments will consist of recording of all adverse events, and regular monitoring of haematology and blood chemistry parameters, and vital signs. These parameters are evaluated during the patients' follow-up visits.

Study results will be presented in tabular format. Two sided 95% exact confidence intervals will be presented where required. Continuous variables will be summarized by a mean, standard

	TRI-REPAIR – Tricuspid Regurgitation RePAIR with Cardioband Transcatheter System (TR1-1). Study protocol	
---	---	---

deviation, minimum, median and maximum. Categorical variables will be summarized by a count and percentage. If statistical tests will be done the significance level will be equal to or lower than 5%. Nominal p-values will be presented. Where confidence limits are appropriate, the confidence level will be 95%.

Baseline demographic and other baseline characteristics, together with safety analyses will be performed on all subjects.

The numbers of subjects who entered and completed each visit of the study will be provided, as well as the reasons for all discontinuations, grouped by major reason (e.g., lost to follow-up, adverse event, etc.). A list of discontinued subjects, protocol deviations, and subjects excluded from the efficacy analysis will be provided.

Descriptive statistics will be provided for the efficacy and safety outcome results.

The analysis of all adverse events will include incidence tables and incidence tables by severity, relationship to treatment and baseline parameters. Serious adverse events will be listed and discussed individually.

6 SUBJECT ENROLMENT

The inclusion and exclusion criteria listed below must be used for the purpose of enrolling patients into this clinical investigation.

6.1 Inclusion criteria

Patients who participate in this study must meet all of the following inclusion criteria:

1. chronic functional tricuspid regurgitation (FTR) 2+ to 4+ on a scale of 4+ (moderate to severe) with annular diameter ≥ 40 mm with valve Systolic pulmonary pressure (sPAP) ≤ 60 mmHg
2. ≥ 18 years old
3. New York Heart Association (NYHA) Class II-IVa
4. Symptomatic despite Guideline Directed Medical Therapy (GDMT); at minimum patient on diuretic regimen
5. LVEF $\geq 30\%$
6. Patient is willing and able to comply with all specified study evaluations
7. The Local Site Heart Team concur that surgery will not be offered as a treatment option
8. Transfemoral access of the Cardioband is determined to be feasible

6.2 Exclusion criteria

Patients who fulfill any of the following criteria may not participate in this study.

1. Aortic, mitral and/or pulmonic valve stenosis and/or regurgitation \geq moderate
2. Severe uncontrolled hypertension (SBP ≥ 180 mmHg and/or DBP ≥ 110 mm Hg)
3. Previous tricuspid valve repair or replacement
4. Presence of trans-tricuspid pacemaker or defibrillator leads which cause impingement of the tricuspid valve leaflet as evaluated by echocardiography.

5. Active endocarditis
6. MI or known unstable angina within the 30 days prior to the index procedure
7. Any PCI or transcatheter valvular intervention within 30 days prior to the index procedure
8. Hemodynamic instability or on IV inotropes
9. Cerebrovascular Accident (CVA) within the past 6 months
10. Subject is on chronic dialysis
11. Anemia (Hb < 9 g/L) not corrected by transfusion
12. Bleeding disorders or hypercoaguable state
13. Active peptic ulcer or active gastrointestinal (GI) bleeding
14. Contraindication to anticoagulants
15. Known allergy to stainless steel, nickel, and/or polyester
16. Pregnant or lactating; or female of childbearing potential with a positive pregnancy test 24 hours before any study-related radiation exposure
17. In the judgment of the Investigator, co-morbid condition(s) that could limit the subject's ability to participate in the study, including compliance with follow-up requirements, or that could impact the scientific integrity of the study
18. Life expectancy of less than 12 months
19. Impaired judgment and/or is undergoing emergency treatment
20. Currently participating in another investigational drug or device study that has not completed the primary endpoint or that clinically interferes with the endpoints of this study
21. Intra-cardiac masses, thrombi or vegetations
22. Patients with cardiac cachexia
23. Subjects in whom transesophageal echocardiography is contraindicated
24. Known hypersensitivity or contraindication to procedural medications which cannot be adequately managed medically
25. Untreated clinically significant CAD requiring revascularization
26. Echocardiographic evidence of severe right ventricular dysfunction
27. Any coronary or endovascular surgery, within 3 months prior to procedure

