Exclusion Criteria	
 1. Aortic, mitral and/or pulmonic valve stenosis and/or regurgitation \geq moderate 2. Severe uncontrolled hypertension (SBP \geq 180 mmHg and/or DBP \geq 110 mm Hg) 3. Previous tricuspid valve repair or replacement 4. Presence of trans-tricuspid pacemaker or defibrillator leads which cause impingement of the tricuspid valve leaflet as evaluated by echocardiography. 5. Active endocarditis 6. MI or known unstable angina within the 30 days prior to the index procedure 7. Any PCI or transcatheter valvular intervention within 30 days prior to the index procedure 8. Hemodynamic instability or on IV inotropes 9. Cerebrovascular Accident (CVA) within the past 6 months 10. Subject is on chronic dialysis 11. Anemia (Hb $<$ 9 g/L) not corrected by transfusion 12. Bleeding disorders or hypercoaguable state 13. Active peptic ulcer or active gastrointestinal (GI) bleeding 14. Contraindication to anticoagulants 15. Known allergy to stainless steel, nickel, and/or polyester 16. Pregnant or lactating; or female of childbearing potential with a positive pregnancy test 24 hours before any study-related radiation exposure 17. In the judgment of the Investigator, co-morbid condition(s) that could limit the subject's ability to participate in the study, including compliance with follow-up requirements, or that could impact the scientific integrity of the study 18. Life expectancy of less than 12 months 19. Impaired judgment and/or is undergoing emergency treatment 20. Currently participating in another investigational drug or device study that has not completed the primary endpoint or that clinically interferes with the endpoints of this study

	TRI-REPAIR – Tricuspid Regurgitation RePAIR with CaRdioband Transcatheter System (TR1-1). Study protocol	
---	---	---

	
 21. intra-cardiac masses, thrombi or vegetations 22. Patients with cardiac cachexia 23. Subjects in whom transesophageal echocardiography is contraindicated 24. Known hypersensitivity or contraindication to procedural medications which cannot be adequately managed medically 25. Untreated clinically significant CAD requiring revascularization 26. Echocardiographic evidence of severe right ventricular dysfunction 27. Any coronary or endovascular surgery, within 3 months prior to procedure

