7 STUDY VISITS AND PROCEDURES

The study will commence following institutional medical ethics committee and regional competent authority approval. Study evaluation continues until 24 months of follow up post implantation has been obtained on all available participating subjects.

Screening of patients will be performed according to the hospital standard screening for tricuspid valve repair and replacement. In addition, patients will be screened for their suitability for Cardioband therapy. A central eligibility committee will be established to determine final enrolment of patients across all investigational sites. The eligibility committee will include at least a Heart Failure specialist, and an Echocardiography specialist. Patients will give a written consent for health information release prior to screening process. The treatment procedure will be performed according to the instructions outlined in the current approved IFU.

Data will be collected at the following time points (as expected in the course of a surgical treatment): baseline, procedure, discharge and clinical follow-up at 30 days, 6 months, 12 months and 24 months from index procedure. Data from any other additional time points may be collected and analyzed if available.

The procedures associated with each study visit are outlined and summarized in **Table 4**.

TRI-REPAIR – Tricuspid Regurgitation RePAIR with Cardioband Transcatheter System (TR1-1). Study protocol

Procedure	Screening	Baseline	Implantation	Discharge	30 days	6, 12, 24 months
Visit Number	-1	0	1	2	3	4
Range	- 1 month	- 1 month	0	NA	-1 wk/+ 2 wks	+/- 1 month
Data release Consent	X					
Study informed consent		X				
Demographics		X				
Wearable data watch		X	X	X	X	X
Medical History		X				
Routine Blood tests		X		X	X	X
Pregnancy test (if applicable)		X				
General Clinical State		X		X	X	X
Adverse Events		X	X	X	X	X
Medication Profile		X		X	X	X
Tricuspid Regurgitation Assessment by TTE	X	X		X	X	X
Tricuspid Regurgitation Assessment by TEE		X	X			
Tricuspid valve anatomy (by Echo and/or CT)	X					
Coronary Angiography (within the past 12 months, optional)	X					
Cardiac MRI (optional)	X					X
6-minute walk test		X			X	X
QoL questionnaire (KCCQ)		X			X	X
NYHA Functional Class		X			X	X
Cardioband Implantation			X			

Table 4: Schedule of Visits and Procedures

	TRI-REPAIR – Tricuspid Regurgitation RePAIR with CaRdioband Transcatheter System (TR1-1). Study protocol	[REDACTED] [REDACTED] [REDACTED]
---	---	--

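### Exclusion 11 sets the anaemia limit at Hb < 9 g/L (0.9 g/dL), almost certainly a slip for 9 g/dL (90 g/L), so as printed it excludes no realistic candidate

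*Protocol*

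**What the plan says.** Exclusion 11 in Protocol section 6.2 is "Anemia (Hb < 9 g/L) not corrected by transfusion". The exclusion list in the synopsis (section 1) carries the same value and unit: "9 g/L) not corrected by transfusion".

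Section 6 makes the lists mandatory: "The inclusion and exclusion criteria listed below must be used for the purpose of enrolling patients into this clinical investigation". Section 6.2 adds that meeting any single exclusion bars a patient.

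The other places that touch on haemoglobin or anaemia set no limit:

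- Protocol 5.5.3 plans "regular monitoring of haematology and blood chemistry parameters, and vital signs".
- Table 4 in Protocol section 7 schedules "Routine Blood tests" at baseline, discharge and each follow-up visit.
- SAP 4.1.5 lists chronic anaemia among the baseline risk factors to be tabulated, with no value or unit.

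**The concern.** The printed limit is too low to act as an exclusion. Candidates are in NYHA class II to IVa, must be able to comply with the study evaluations, and do a 6-minute walk test at baseline. Patients who are haemodynamically unstable or under emergency treatment are excluded separately. Nobody left in that pool will have a haemoglobin below 0.9 g/dL. The qualifier about transfusion also shows that the authors had ordinary, treatable anaemia in mind, which fits a limit of 9 in g/dL and not in g/L.

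Three things depend on the line:

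- **Safety.** Protocol 9.3 lists bleeding that needs transfusion, gastrointestinal bleeding, haemolysis and bleeding related to anticoagulants among the anticipated events. The criterion meant to keep out patients with uncorrected anaemia does not do so as printed.
- **Compliance.** Protocol 11.7 defines a deviation as a failure to follow the plan's requirements. Enrolling a patient with an uncorrected haemoglobin of 70 g/L complies with the printed text and breaches the likely intended one, so a monitor has no clear written basis for a decision.
- **Analysis set.** SAP 2.3 restricts the ITT cohort to subjects who satisfied the eligibility criteria, and the as-treated cohort is drawn from it. For a subject in the disputed range, cohort membership depends on which limit applies.

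**Working it through.** **Inputs**

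- Printed limit: Hb < 9 g/L (Protocol 6.2, exclusion 11, and the synopsis).
- Conversion: 1 g/dL = 10 g/L.
- Likely intended limit: Hb < 9 g/dL. This is an inference. The documents do not state it.
- Example haemoglobin values of 50, 70 and 85 g/L. These are illustrations, not figures from the documents.

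**Step 1: convert the limits**

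- Printed: 9 g/L ÷ 10 = 0.9 g/dL.
- Likely intended: 9 g/dL × 10 = 90 g/L.
- Ratio: 90 ÷ 9 = 10.

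**Step 2: apply both limits to the example patients**

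| Hb (g/L) | Hb (g/dL) | Multiple of the printed limit | Excluded if < 9 g/L? | Distance below 90 g/L | Excluded if < 90 g/L? |
|---|---|---|---|---|---|
| 50 | 5.0 | 50/9 = 5.6 | No | 90 − 50 = 40 | Yes |
| 70 | 7.0 | 70/9 = 7.8 | No | 90 − 70 = 20 | Yes |
| 85 | 8.5 | 85/9 = 9.4 | No | 90 − 85 = 5 | Yes |

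The two readings disagree for every uncorrected value from 9 g/L up to, but not including, 90 g/L.

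**Step 3: could the unit be an artefact of reading the PDF?** This is unlikely. The same unit appears in two separate lists, and nothing in the line is redacted.

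**Step 4: does other text supply the missing limit?** The visible text does not. The haematology monitoring, the scheduled blood tests and the SAP's risk-factor table all lack a threshold. Other exclusions would catch some anaemic patients for other reasons:

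- haemodynamic instability or IV inotropes (8)
- bleeding disorders (12)
- active ulcer or gastrointestinal bleeding (13)
- contraindication to anticoagulants (14)
- investigator judgement on co-morbidity (17)
- "Life expectancy of less than 12 months" (18)
- "Impaired judgment and/or is undergoing emergency treatment" (19)

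None of them sets a haemoglobin value, and 14, 18 and 19 bear only loosely on anaemia. Section 7 also provides that "A central eligibility committee will be established to determine final enrolment of patients across all investigational sites", but that committee too is given no haemoglobin limit.

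**The case against.** The best counter-argument accepts that the unit is wrong and holds that the error is only editorial. Any clinician would read g/dL. Haemoglobin enters no endpoint, sample-size argument or stopping rule. Further safeguards exist: Protocol section 7 has candidates go through the hospital's usual screening for tricuspid repair and replacement, and section 8.1 has the principal investigator or interventional cardiologist assess contraindications to transfemoral access. The Instructions for Use hold further contraindications and are not available here.

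Much of this stands. It is why the practical impact is rated as small, and why the statement that no other limit exists covers only the visible text. The chronic anaemia item in SAP 4.1.5 should carry no weight either way. The same list includes ongoing inotropic support, although exclusion 8 bars IV inotropes, so it looks like a generic history list. The deviation and cohort problems are consequences of the same unit error, not separate faults.

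The objection does not remove the point. The error sits in a decision threshold of a binding safety criterion, not in background text. Relying on each reader to correct it silently is a poor substitute for a numeric limit applied in the same way at six sites. The safeguards that can be seen rest on judgement and state no haemoglobin value.

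**Conclusion.** Exclusion 11 is wrong as written in both lists. The printed limit is one tenth of the likely intended one, and as printed it excludes no realistic candidate.

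The conclusion rests on two assumptions. The first is general physiology: candidates for this procedure do not have a haemoglobin below 0.9 g/dL. The second is that 9 g/dL was meant. That is a strong inference from the number and the transfusion qualifier, and the sponsor should confirm it.

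The practical impact is probably small. The documents do not say how many candidates have an uncorrected haemoglobin between the two limits, and it may be none. No effect on event rates is claimed. The correction should still be made, because the line is a safety criterion and the change costs almost nothing.

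**What to change.** Ask the sponsor to confirm the intended value. Then change exclusion 11 in the synopsis and in Protocol section 6.2 to: *Anaemia, Hb < 9 g/dL (90 g/L), not corrected by transfusion*. Giving both units prevents the slip from recurring.

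If enrolment is open, tell the sites and the central eligibility committee at once which limit applies. If it has closed, a short clarification should record which limit was used, so that deviations and membership of the SAP 2.3 cohorts can be settled. The enrolment dates are not visible in the protocol.

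The cost is two lines of text and one notice, with no effect on design, sample size or analysis methods. The change should go through the amendment route in Protocol 11.2 as appropriate. The documents do not settle whether formal re-approval is needed: Protocol 11.1 requires Ethics Committee approval for changes that may raise risk or harm validity, and on its face a stricter limit does neither.

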Procedure	The system will be delivered percutaneously via the femoral vein. The procedure will be guided by fluoroscopy and trans-esophageal / intracardiac echocardiography
Follow-Up Schedule	1 month: 30 ± 14 days 6 Months: 180 ± 30 days 12 Months: 365 ± 30 days 24 Months: 730 ± 30 days Subjects in whom no devices are implanted will be followed for 6 months.
Follow Up Evaluations	Key Pre-Implantation Procedures: 
 1. History and Physical 2. TTE , TEE and/or CT angiography and/or MRI 3. 6 minute walk test 4. KCCQ Key Post-Procedure Procedures: 
 1. Serial AE assessment, history, and physical at 30 days, 6 months, 12 months, 24 months) 2. Serial TTEs (30 days, 6 months, 12 months, 24 months) 3. Cardiac MRI at 6 months (optional) 4. 6 minute walk tests (30 days, 6 months, 12 months, 24 months) 5. KCCQ
Clinical Event Committee	An independent Clinical Event Committee will adjudicate all Serious Adverse events.
First subject in	
Last subject in	

	TRI-REPAIR – Tricuspid Regurgitation RePAIR with Cardioband Transcatheter System (TR1-1). Study protocol	[REDACTED] [REDACTED] [REDACTED]
---	---	--

Last follow-up	[REDACTED] [REDACTED] [REDACTED]
----------------	----------------------------------

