5 INVESTIGATION DESIGN & ENDPOINTS

5.1 Clinical Study Overview

This clinical investigation is a single arm, multi-center, prospective study with intra-patient comparisons.

Candidates for Cardioband TR treatment are symptomatic patients with functional tricuspid valve repair. Patients are selected upon clinical conditions and severity of TR. Anatomical feasibility is assessed by Echocardiography and/or other exams (such as CT and angiography) according to the site common practice. Patients will be screened and enrolled according to the study inclusion and exclusion criteria.

Patients will undergo tricuspid valve repair with Cardioband implanted via transcatheter procedure under Transoesophageal / Intracardiac echocardiography (TEE/ICE) and fluoroscopy guidance. Post-procedure clinical care will be performed according to standard management of valve repair; Clinical follow-up including standard post-procedural management of surgical valve repair and Transthoracic Echo (TTE) assessment of the degree of Tricuspid regurgitation will be obtained at hospital discharge, 30 days, 6, 12 and 24 months post-index procedure.

As the follow up at 30 days is of most importance in terms of the patient's safety: The first 3 patients will have to complete 30 days follow up before the recruitment of additional patients. In related to the first 3 patients, recruitment will continue in case of elongated hospitalization or complications that are unrelated to the study device as will be judge by the study clinical event committee.

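### Table 4 does not ensure the pregnancy-test timing in exclusion 16: its only test is at Baseline, up to about a month before the fluoroscopy-guided implantation

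*Protocol*

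**What the plan says.** Protocol Section 6.2, item 16, excludes pregnant or lactating women and, separately, a "female of childbearing potential with a positive pregnancy test 24 hours before any study-related radiation exposure". The synopsis repeats the item in the same terms ("positive pregnancy test 24 hours before any study-related radiation exposure").

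Table 4 in Section 7 carries one row for the test, "Pregnancy test (if applicable"), with a single mark under Baseline (visit 0). Screening (visit -1) and Baseline both have a range of minus one month; Implantation (visit 1) is at time zero. There is no pregnancy-test mark under Screening or Implantation, and no other section schedules or repeats the test.

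Three procedures in the protocol involve, or may involve, radiation:

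- Implantation. The synopsis, Section 5.1 and Section 8.1 all describe guidance by fluoroscopy.
- Valve anatomy, marked at Screening only: "Tricuspid valve anatomy (by Echo and/or CT").
- Coronary angiography, marked at Screening only: "Coronary Angiography (within the past 12 months, optional").

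On the screening imaging, Section 5.1 says: "Anatomical feasibility is assessed by Echocardiography and/or other exams (such as CT and angiography) according to the site common practice". The synopsis lists pre-implantation imaging as "TTE , TEE and/or CT angiography and/or MRI".

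**The concern.** A schedule of visits is what site staff work from. Here it gives one test, while the criterion refers to any study-related exposure and sets a 24-hour reference point. A site can complete every mark in Table 4 and still take a woman of childbearing potential to fluoroscopy on a test that is weeks old. A pregnancy that arises or becomes detectable between Baseline and the procedure would not be picked up by any scheduled test.

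The check can apply in this trial. Section 6.1 admits adults from age 18 with no upper age limit and no restriction by sex. Section 11.5 requires consent to cover risk to an embryo or foetus, and Section 10.2 lists foetal harm among the criteria for a serious adverse event. What is at stake is a safety exclusion that sites may apply differently, with avoidable protocol deviations. The statistical analysis is not affected.

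**Working it through.** No sample-size, power or error-rate figure is involved, so the check sets the criterion beside the schedule.

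**Inputs**

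- Reference time in exclusion 16: 24 hours (Section 6.2; synopsis).
- Scheduled tests: one, at Baseline (Table 4).
- Baseline range: minus one month, with no minimum gap before Implantation (Table 4).
- Radiation at Implantation: always (synopsis, Sections 5.1 and 8.1).
- Radiation at Screening: possible but not required (Table 4, Section 5.1).
- Assumptions: one month is about 30 days; the criterion means within 24 hours; visits occur in the order in which Table 4 numbers them.

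**Age of the test at implantation**

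Let d be the days from Baseline to Implantation. Table 4 allows d from 0 to about 30.

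Age of test in hours = 24 × d.

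At the outer limit: 24 × 30 = 720 hours, which is 720 / 24 = 30 times the reference time. The criterion is met for fluoroscopy only if 24 × d ≤ 24, that is, d ≤ 1.

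**Routes through the schedule**

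| Route permitted by Table 4 | Screening exposure covered? | Implantation covered? |
|---|---|---|
| (a) Echo-only screening, or angiogram already on file; Baseline within 24 hours of implantation | No study exposure to cover | Yes |
| (b) Same screening; Baseline more than 24 hours before implantation | No study exposure to cover | No |
| (c) Study-related CT or angiography done at Screening | No: the test comes at the later visit | Only if d ≤ 1 |

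Route (a) satisfies both texts. Route (b) follows the schedule and misses the criterion at the one exposure that every treated subject has. In route (c) one test at Baseline cannot serve both an earlier exposure and the implantation. Table 4 permits all three routes and does not direct sites to (a).

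**The case against.** A reader might infer that exclusion 16 is impossible to meet by following Table 4, or that following the table means an untested screening CT. The documents do not support either reading.

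- The Baseline range is an outer limit, so a Baseline visit the day before the procedure is allowed. This stands, and is route (a).
- CT is an alternative to echo, and angiography is optional and may be up to 12 months old. No screening radiation is required. This stands.
- Screening imaging may not be study-related at all. Section 5.1 leaves it to site practice, and Section 7 says: "Screening of patients will be performed according to the hospital standard screening for tricuspid valve repair and replacement". Table 4 marks only a data-release consent at Screening, with study consent at Baseline, which fits a review of routine-care images. This stands in part: Section 7 adds screening for suitability for the device, and the protocol never says what counts as study-related, so sites can read it either way.
- Pregnant women are excluded whatever the test timing, the criteria in Section 6 are mandatory, and nothing forbids a later test. A dated result also makes the timing checkable. All true, but a mandatory criterion does not cure a schedule that puts its only test elsewhere.
- The criterion is loosely worded: it excludes on a positive result 24 hours before exposure, without saying within 24 hours or expressly ordering a test. That softens the contradiction. It also leaves Table 4 as the only operating instruction, and the table does not carry the 24-hour timing.

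**Conclusion.** The point holds in a limited form. Table 4 does not ensure the timing in exclusion 16. Its single test may be up to about 30 days old at a fluoroscopy-guided implantation, and it comes after any study-related CT or angiography done at Screening. Compliance with both texts is possible but depends on how a site happens to book its visits.

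The number of women concerned cannot be derived. The documents give no age or sex mix for the planned 60 subjects; it is probably small and could be zero. No endpoint, analysis or sample size changes. The conclusion rests on reading the criterion as within 24 hours and, for the screening part, on the imaging being study-related, which the protocol leaves open. It is a mismatch on a safety exclusion that should be corrected, and it is not a threat to the trial's results.

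**What to change.** Reconcile exclusion 16 (Section 6.2 and the synopsis) with Table 4, so that the criterion and the schedule state the same test timing relative to study-related radiation. Either text may move; the sponsor and investigators decide which timing stands. In the same amendment, say whether CT and angiography done at Screening count as study-related, and make the wording of the criterion explicit about the time window and whether a test is required.

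The cost is an edit to one table row or one criterion. If the criterion's timing is kept, some women of childbearing potential may need the test repeated; no one else is affected.
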